#### Ultra-high-frequency ECG analysis

High frequency bandwidth ECG data obtained via ambulatory ECG recordings will also be processed to extract high frequency components for signal averaged UHF-ECG analysis. This will be used to investigate for characteristic UHF-ECG profiles synonymous with underlying Brugada syndrome.

#### Manual ECG review with physiological and activity data

We will also manually analyse ECG recordings coinciding with day to day physiological stressors using activity diaries to look for transient manifestations of concealed arrhythmia syndromes.

#### Study C: Arrhythmic risk stratification using UHF-ECG

This protocol will encompass participants recruited to Groups A-C

#### Protocol

Participants will undergo the consent process and testing during their initial research visit. The steps will include the following:

- Participants will be counselled regarding the research study and written informed consent will be obtained.
- All participants will undergo a 12-lead ECG and ultra-high-frequency ECG recording for up to 5 minutes in duration.
- Patients will be followed up prospectively for instances of ventricular arrhythmias, aborted cardiac arrest or sudden cardiac death.

#### Ultra-high-frequency ECG analysis

We will utilise computational modelling to determine the degree of QRS fractionation within the UHF-ECG profile. We will also investigate the role of other metrics and parameters to analyse UHF-ECG fragmentation. These data will be used to assess the value of QRS fractionation as a surrogate for arrhythmic risk in patients with underlying inherited arrhythmic or arrhythmogenic conditions.

#### Burdens/Risks:

There are no significant risks entailed within this non-invasive study. A potential burden will be the requirement to wear an ambulatory ECG monitor semi-continuously over a 3 month period, as participants must remain motivated and engaged. We expect that participants will not always be wearing the monitoring devices and as part of the study, we will be assessing acceptability, user-friendliness, practicality and participant comfort using feedback from research participants. The adhesives used for the ECG electrodes can cause skin irritation or redness in some participants and non-allergic adhesive preparations may be required.

### 3.4 STUDY OUTCOME MEASURES

**Commented [BK4]:** Outcome measures differ to IRAS a57/58. No mention of AI algorithm here

**Commented [KS5R4]:** Sorry, neural network and AI algorithm used interchangeably. Neural network is jargon

#### Primary Outcome Measures

- Sensitivity, specificity and AUC value for neural networks 1 and 2 to detect the Brugada ECG pattern in 12-lead ECGs.

- Yield of extended duration ambulatory ECG monitoring to detect the Brugada ECG pattern in patients with concealed Brugada syndrome, using neural networks 1 and 2.
- Sensitivity, specificity and AUC value for neural network 3 to diagnose concealed Brugada syndrome from 12-lead ECGs
- Sensitivity, specificity and AUC value for neural network 4 to diagnose an SCN5a mutation from 12-lead ECGs.
- Yield of extended duration ambulatory ECG monitoring to detect the Brugada ECG pattern (neural networks 1 and 2) and LQTS manifestation in patients with idiopathic VF.

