## STUDY SUMMARY

TITLE	Unmasking Concealed Arrhythmia Syndromes
DESIGN	Proof-of-concept studies to develop ECG AI algorithms, followed by case-control diagnostic accuracy study and prospective cohort studies
AIMS	
 
1. To develop machine learning algorithms for 12-lead ECGs to detect diagnostic features of Brugada syndrome.
 
2. To test and validate these algorithms prospectively in participants wearing ambulatory ECG recording devices.
 
3. To ascertain the role of UHF-ECG for risk stratification in patients with inherited arrhythmogenic conditions
 

OUTCOME MEASURES	
 
• Brugada ECG algorithm sensitivity, specificity and AUC value for both 12 lead ECGs and 12 lead vest ECGs
 
• Yield of extended duration multi-electrode ambulatory ECG monitoring to detect the Brugada ECG pattern in concealed Brugada syndrome
 
• The utility of extended duration multi-electrode ambulatory ECG monitoring to detect a single case of underlying Brugada or LQTS manifestation in idiopathic VF
 

POPULATION	Healthy volunteer controls, patients with a diagnosis of Brugada syndrome, patients with a diagnosis of idiopathic VF syndrome and patients with other inherited arrhythmogenic conditions
ELIGIBILITY	
Participant sets (Appendix 1):
 
 
• Group A – healthy volunteers
 
• Group B – concealed arrhythmia syndrome patients (patients with a normal ECG with a known underlying arrhythmic diagnosis)
 
• Group C – manifest arrhythmia syndrome patients (patients with an arrhythmic syndrome with an abnormal ECG)
 

DURATION	November 2023 – November 2026 (3 years)

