### Study B: Remote arrhythmia diagnostics

In this study, we will undertake validation studies to assess the robustness, accuracy and applicability of the aforementioned AI algorithms (i.e. neural networks) on ECG recordings from several different ambulatory monitoring modalities. This protocol will encompass participants recruited in Groups A-C.

Commented [KS1]: Added for clarity

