### Application of ECG AI to ECG recordings

ECG recordings will be downloaded onto local storage. The digital ECGs will be processed and denoised using specialized algorithms developed by the research team. The previously developed ECG AI algorithms for Brugada syndrome will subsequently be applied to the cleaned ECG recordings for all patient groups.

We will establish the sensitivity for the Brugada classification algorithms on recordings from patients with manifest Brugada syndrome (Group C) and their specificity using the recordings from the healthy volunteers (Group A). The algorithms will also be applied to

patients with concealed arrhythmia syndromes (Group B) to determine the diagnostic yield of different ambulatory ECG recording modalities for different time durations. We will apply both the in-house developed Brugada ECG AI algorithms as well as existing ECG AI algorithms developed by external academic or industry collaborators, to investigate for underlying concealed arrhythmias.

**Commented [BK2]:** From this description I think this should be a Pre-clinical device development or performance testing medical device study (no MHRA review required)

**Commented [KS3R2]:** I have amended project filter q2 on IRAS to reflect

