## 6. ASSESSMENT & FOLLOW UP

Patients will be followed up over a 3 month period remotely while wearing their ambulatory ECG. 12-lead ECG and UHF-ECG data will be collected at the index visit. Symptom diaries and ambulatory ECG recordings will be collected at the end of the study interval. Any incidental findings that we identify during the study will be reviewed by the research team and reported to the GP and also the cardiology team normally looking after the patient. We will continue to follow up all patients after their last contact with the research team through review of the electronic health record and any clinical cardiac device checks up until the end of the study on 1st April 2027, at which time all follow up will cease. The prospective studies

will end after 200 patients have undergone the 3 month interval of follow up or by the study end date of 1st April 2027.

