We are also seeking to identify at least one extra patient with Long QT or Brugada syndrome by performing extended duration monitoring beyond standard 12 lead 24-hour Holter. Registry data (7–9) suggests that between 3–4% of idiopathic VF patients eventually receive a specific diagnosis of Brugada syndrome through conventional diagnostic testing and routine clinical follow up. A similar proportion are diagnosed with long QT syndrome. If extended duration monitoring can identify half of these (4%), then 50 patients will provide 87% power to detect at least one extra case (simulated through repeat sampling of a binomial distribution).

We also plan to recruit 100 patients with other inherited arrhythmic conditions, who can be subdivided into high and low arrhythmic risk groups. We believe that these cohort sizes will be adequate to gather sufficient pilot data to enable identification of subtle changes in UHF-ECG profiles.

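### Two primary Brugada yields are read by networks 1 and 2, with no rule that confirms a flag or sets the yield against a false-flag rate, so false flags can count as yield

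*Protocol*

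**What the plan says.** Section 3.4 of the protocol (Primary Outcome Measures) makes two Brugada yields primary. One is the yield for the Brugada ECG "pattern in patients with concealed Brugada syndrome, using neural networks 1 and 2". The other is the yield in idiopathic VF, where the same two networks read the Brugada part; the LQTS part is not tied to them.

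Section 3.3 (Application of ECG AI to ECG recordings) applies the algorithms to Group B "to determine the diagnostic yield of different ambulatory ECG recording modalities for different time durations". The same paragraph takes sensitivity from manifest Brugada patients and, for the algorithms, "their specificity using the recordings from the healthy volunteers (Group A"). Study B's monitoring covers all groups: "This protocol will encompass participants recruited in Groups A-C".

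The Study Summary lists as an outcome measure the utility of extended monitoring "to detect a single case of underlying Brugada or LQTS manifestation in idiopathic VF". Section 7 sizes that part of the study: at a 4% rate, "50 patients will provide 87% power to detect at least one extra case". Section 7 also plans an accuracy on prolonged recordings, counted in patients, that discriminates healthy volunteers from manifest Brugada patients (95% assumed against a target above 85%, 90 patients).

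Three provisions involve human review:
- Study A has expert majority labelling of the ECG dataset used to train and validate the networks.
- Section 3.3 has manual review of periods picked out by activity diaries.
- Section 6 states "Any incidental findings that we identify during the study will be reviewed by the research team and reported to the GP".

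**The concern.** A yield counts detections, so it depends on what counts as one. Here the named reader is a pair of networks run over recordings of up to 3 months, and no step separates a true Brugada pattern from a false flag. None of the three review provisions does so: the first concerns the Study A ECGs, the second is prompted by diary entries and not by flags, and the third concerns clinical communication and does not define yield.

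An unconfirmed false flag can only raise the yield, which is the direction of the study hypothesis. In concealed Brugada the patients already carry the diagnosis, so a false flag inflates the yield of the monitoring but is not a false diagnosis. In idiopathic VF it would look like a new Brugada diagnosis, in a group where very few true ones are expected.

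**Working it through.** **Inputs from the protocol (section 7).** Idiopathic VF: n = 50, rate of additional Brugada or LQTS cases 4%, power 87%. Healthy volunteers: 50 to be recruited. Accuracy calculation: 95% in 90 patients.

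**Assumptions.** The documents give no patient-level false-flag rate, so f is taken as 1%, 2%, 4% and 5%. The 4% is split evenly between Brugada and LQTS, that is 2% each.

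**1. The plan's own figure.** P(at least one true case) = 1 − (1 − 0.04)^50 = 1 − 0.130 = 0.870. The stated 87% reproduces. It treats every detection as true.

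**2. False flags alone, no true case.** P(at least one positive in 50) = 1 − (1 − f)^50:

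| f | (1 − f)^50 | P(at least one) |
|---|---|---|
| 1% | 0.605 | 40% |
| 2% | 0.364 | 64% |
| 4% | 0.130 | 87% |
| 5% | 0.077 | 92% |

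At f = 4% the chance of a positive with no true case equals the planned power.

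**3. Expected share of Brugada positives that are true.** Expected true = 50 × 0.02 = 1.0. Expected false = 49 × f. Share = 1.0 / (1.0 + 49f), a ratio of expected counts:

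| f | Expected false | True share |
|---|---|---|
| 1% | 0.49 | 1/1.49 = 67% |
| 2% | 0.98 | 1/1.98 = 51% |
| 5% | 2.45 | 1/3.45 = 29% |

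**4. Does the planned accuracy settle f?** No. With 45 healthy and 45 manifest patients, 95% accuracy means 0.05 × 90 = 4.5 errors. If all fall in the manifest group, f = 0%. If all fall in the healthy group, f = 4.5/45 = 10%. The pooled figure neither fixes f nor rules out the range above.

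**5. What the sample can show.** Exact (Clopper-Pearson) 95% intervals: 1/50 gives 0.05% to 10.6%, and 2/50 gives 0.5% to 13.7%. No flags among 50 healthy volunteers still leaves an upper limit of 1 − 0.025^(1/50) = 7.1%. One unconfirmed flag in 50 idiopathic VF patients therefore cannot be told apart from a false-flag rate that a clean Group A would still allow.

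**The case against.** The strongest reply is that this is silence and not error. Naming the networks as the tool does not say that an unreviewed flag is a case, and a positivity rule and over-read could sit in an SAP that is not shown. Section 7 also words the idiopathic VF target as patients with a syndrome and benchmarks it to registry diagnoses, which points to true cases. These points carry weight. But what counts as a detection belongs to the definition of a primary outcome, and the protocol defines these two by network output and offers no other criterion.

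A second reply is that a false-positive estimate is already planned: Group A specificity, plus a patient-level accuracy on prolonged recordings that includes healthy volunteers. This is right, and it narrows the point. A reader might infer that specificity would come from shorter wear than the yields. The documents do not support that: the accuracy is planned on prolonged recordings, and Group A follows the same Study B procedures. What remains is that the accuracy pools healthy and manifest participants, and neither figure is linked to the yields. Actual exposure may also differ between groups, since devices depend on availability and "We expect that participants will not always be wearing the monitoring devices".

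A third reply is that expert confirmation changes the outcome from network yield to network-plus-expert yield and adds reading work. That is true. It is why confirmation is asked for at least in idiopathic VF, and why the unconfirmed yield should be reported as well.

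**Conclusion.** The point holds. As written, false flags from networks 1 and 2 count towards the concealed Brugada yield and the Brugada part of the idiopathic VF yield. The effect is most serious in idiopathic VF, where about one true Brugada case is expected. At assumed false-flag rates of 1%, 2% and 5%, only 67%, 51% and 29% of Brugada positives would be true, given the assumed even split of the 4%. The size rests on those assumptions, because the documents give no false-flag rate; the direction does not. It should be fixed, at modest cost, before the ambulatory recordings are read.

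Three stronger readings are not supported. The 87% is not wrong: it is correct as a planning figure for true detections. The LQTS part is not implicated, since it is not tied to these networks. A reader might also infer that the McNemar comparison of Holter with prolonged recordings is biased, but section 7 does not say that the networks read those paired recordings.

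**What to change.** 1. Apply one patient-level positivity rule to Group A and to the yield groups, at the recording durations used for the yields. Report the Group A flag rate with its exact 95% CI beside each Brugada yield, broken down by device only where the data allow. This uses recordings already planned.
2. Report the idiopathic VF result as a yield with its exact 95% CI. Keep the target of one or more additional cases for sample-size planning only, and align the Study Summary wording with section 3.4.
3. At least in idiopathic VF, count a flag as a Brugada detection only after the existing experts have reviewed the flagged segment blind to group and device. Report the unconfirmed network yield too, so that it can be compared like for like with the Group A flag rate. Including flagged Group A segments in the review helps the blinding.

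Cost: a small reading load. As an illustration at f = 5%, idiopathic VF gives 1.0 + 2.45 = 3.45 flagged recordings and Group A gives 50 × 0.05 = 2.5, together 5.95. With five readers, as in Study A, that is about 30 reads at one segment per recording or about 300 at ten. Study A needs at least 3000 × 5 = 15,000. The confirmed yield may be lower than the network yield, and full device matching may not be possible.

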#### **Secondary Outcome Measures**

- Yield of UHF-ECG to detect underlying Brugada syndrome in patients with a concealed ECG phenotype.
- Utility of UHF-ECG for arrhythmia risk stratification in patients with inherited arrhythmogenic conditions
- Beta angle value with highest predictive accuracy for Brugada syndrome based on expert consensus, using regression modelling.
- Identification of novel electrical manifestations that may represent underlying concealed arrhythmia syndromes during day-to-day physiological stressors.
- Clinical endpoints such as ICD therapies, all cause mortality and any clinical events such as hospitalisations or clinical deteriorations.

## **4. PARTICIPANT ENTRY**

### **4.1 PRE-REGISTRATION EVALUATIONS**

Participants will be recruited at Imperial College Healthcare NHS Trust. Participants may be based at other institutions and will be identified via research collaborators.

### **4.2 INCLUSION CRITERIA**

#### **FOR ALL PARTICIPANTS:**

1. Adults willing to take part (ages 18 – 100 years old)
2. Able to give consent

#### **SPECIFIC CRITERIA BY PARTICIPANT SET:**

- Group A – healthy volunteers
- Group B – patients with a normal ECG and an underlying inherited arrhythmic syndrome
- Group C – patients with an arrhythmic syndrome with an abnormal ECG

Further details in Appendix 1.

### **4.3 EXCLUSION CRITERIA**

- Unable to give consent
- Children age < 18 years and adults > 100 years old

### **4.4 WITHDRAWAL CRITERIA**

The research protocol will be terminated early if:

1. Patients lose their capacity to consent or become clinically unstable
2. The patient chooses to withdraw from the study
3. The sponsor, the chief investigator or the research team review the data and decide to stop the study

## 4.5 CONSENT

Commented [BK6]: Please make distinction between Part A and B/C of study

Commented [KS7R6]: done

### Study A

ECG data will be obtained from the host institution (Imperial College Healthcare NHS Trust) as well as external centres both in the UK and internationally. This data will derive from patients identified by the site-specific representatives, who will coordinate secure ECG data transmission and acquisition. All ECG data will be collected anonymously or anonymised at the point of collection. Consent will not be sought as only anonymised ECGs will be obtained. There will be no access to patient-identifiable data from the research team and all data will be fully anonymised prior to transfer.

### Studies B and C

Patients will be identified by members of their direct care team. They may be identified when they attend clinic appointments. Patient records will be reviewed to assess suitability and this will be performed by members of the direct care team. Participation in the study will be discussed with the patients by their direct care team and information will only be passed on to the research team with the patients consent. Verbal consent will be gained by the direct care team for personal contact information to be shared with the research team. This will be documented in the patient notes. The direct care team who discussed the study will make patients aware that participation is voluntary and that if they do not want to participate it will not affect their usual care.

Consent for the study of the prospectively recruited patients will be obtained by a member of the research team. Patients will have details of the study discussed with them and any family members or friends the patients wish to be present. They will also be provided with written information (patient information sheets). Patients will be given as much time as they wish, with a minimum of at least 24 hours, to decide whether they wish to participate in the study and will be offered additional visits to further discuss the study if they wish. Patients are able to withdraw their consent from the study at any time. Patients will be made aware that their participation is voluntary and that if they do not want to take part it will not affect their usual care. Patients who agree to take part in the study will sign a consent form, a copy of the form will be given to the patients and a second copy will be kept in their study record file. A copy will also be kept in the site file.

### Conflicts of Interest:

There are no conflicts of interest to report.

## 5. ADVERSE EVENTS

### 5.1 DEFINITIONS

**Adverse Event (AE):** any untoward medical occurrence in a patient or clinical study participant.

**Serious Adverse Event (SAE):** any untoward and unexpected medical occurrence or effect that:

- **Results in death**
- **Is life-threatening** – *refers to an event in which the participant was at risk of death at the time of the event; it does not refer to an event which hypothetically might have caused death if it were more severe*
- **Requires hospitalisation, or prolongation of existing inpatients' hospitalisation**
- **Results in persistent or significant disability or incapacity**
- **Is a congenital anomaly or birth defect**

Medical judgement should be exercised in deciding whether an AE is serious in other situations. Important AEs that are not immediately life-threatening or do not result in death or hospitalisation but may jeopardise the participant or may require intervention to prevent one of the other outcomes listed in the definition above, should also be considered serious.

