## 5.2 REPORTING PROCEDURES

All adverse events should be reported. Depending on the nature of the event the reporting procedures below should be followed. Any questions concerning adverse event reporting should be directed to the Chief Investigator in the first instance.

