### 5.2.1 Non-serious AEs

All such events, whether expected or not, should be recorded.

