### 5.2.2 Serious AEs

An SAE form should be completed and faxed to the Chief Investigator within 24 hours. However, hospitalisations for elective treatment of a pre-existing condition do not need reporting as SAEs.

All SAEs should be reported to the West of Scotland (REC 5) where in the opinion of the Chief Investigator, the event was:

- 'related', ie resulted from the administration of any of the research procedures; and
- 'unexpected', ie an event that is not listed in the protocol as an expected occurrence

Reports of related and unexpected SAEs should be submitted within 15 days of the Chief Investigator becoming aware of the event, using the NRES SAE form for non-IMP studies. The Chief Investigator must also notify the Sponsor of all related and unexpected SAEs.

Local investigators should report any SAEs as required by their Local Research Ethics Committee, Sponsor and/or Research & Development Office.

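### Section 5.1 makes unexpectedness part of the SAE definition, which does not fit section 5.2.2, where it is a later filter on SAEs

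*Protocol*

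**What the plan says.** Section 5.1 defines an adverse event as "any untoward medical occurrence in a patient or clinical study participant", with no condition on expectedness. It defines an SAE as "any untoward and unexpected medical occurrence or effect" that meets one of five criteria, among them death, threat to life and hospitalisation. A closing paragraph widens the class: "Medical judgement should be exercised in deciding whether an AE is serious in other situations". That paragraph does not mention expectedness.

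Section 5.2 sets a general duty, "All adverse events should be reported", and then a routing rule: "Depending on the nature of the event the reporting procedures below should be followed". Two procedures follow:

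- **5.2.1, non-serious AEs:** "All such events, whether expected or not, should be recorded". No form, recipient or time limit is given.
- **5.2.2, serious AEs:** an SAE form goes to the Chief Investigator within 24 hours, except for elective admissions for a pre-existing condition. SAEs that the Chief Investigator considers both related and unexpected also go to the ethics committee within 15 days, and the Sponsor is notified of them. Unexpected is explained there as "ie an event that is not listed in the protocol as an expected occurrence".

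**The concern.** Seriousness and expectedness are separate attributes of an event. Seriousness should decide whether the Chief Investigator is told quickly. Expectedness should decide which of those events travel further. Section 5.1 merges the two, and section 5.2.2 then applies expectedness a second time.

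What is at stake is prompt oversight. Groups B and C have inherited arrhythmia or cardiomyopathy diagnoses (Appendix 1). The Study C protocol in section 3.3 follows patients for ventricular arrhythmia, aborted arrest and sudden cardiac death. Section 3.4 lists ICD therapies, mortality and hospitalisation among the secondary outcomes. A site could reasonably think of such events as expected in these patients. Under the wording of 5.1 it could then decide that no SAE form is due, before the Chief Investigator, to whom 5.2.2 gives the judgement on relatedness and expectedness, has seen the event.

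**Working it through.** No arithmetic applies: the point depends on no sample size, power figure or event count, and the protocol gives no event rates. The check is to follow events through sections 5.1, 5.2, 5.2.1 and 5.2.2 as worded.

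**Step 1: trace by type of event.**

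| Event | SAE under 5.1? | Procedure that applies | 24-hour form? |
|---|---|---|---|
| Serious, unexpected | Yes | 5.2.2 | Yes |
| Serious, regarded as expected; *non-serious* read in its ordinary sense | No | Neither 5.2.1 nor 5.2.2; only the general duty in 5.2 | No |
| Serious, regarded as expected; *non-serious* read as any AE that is not an SAE | No | 5.2.1, recorded | No |
| Not serious, expected or not | No | 5.2.1, recorded | No |

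The second and third rows are the same event under two readings of the heading of 5.2.1. They differ on whether 5.2.1 catches it. They agree that the SAE form and the 24-hour limit are lost.

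**Step 2: test 5.1 against 5.2.2.** If every SAE is unexpected by definition, requiring SAEs to be unexpected before they go to the ethics committee and Sponsor removes nothing, and only relatedness still filters. Section 5.2.2 is therefore written as though SAEs include expected events, which 5.1 excludes.

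**Step 3: test 5.1 against itself.** The closing paragraph of 5.1 admits important events short of death or hospitalisation as serious with no expectedness condition. Read literally, an expected lesser event may count as serious while an expected death does not. That order cannot be intended.

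**Step 4: ask how many events could be affected.** This depends on what *unexpected* means in 5.1.

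- If the meaning in 5.2.2 carries over, an event is expected only if the protocol lists it as such. The available text has no such list for serious events. The one foreseeable adverse effect it names is skin irritation or redness from the adhesives (Burdens/Risks, section 3.3). On this reading few or no serious events drop out.
- If a site uses its own judgement, which 5.1 does not rule out because it neither defines the word nor refers to 5.2.2, any serious event regarded as expected could drop out. The number cannot be derived.

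**Step 5: repeat the trace with the two words removed from 5.1.** Every event meeting a seriousness criterion becomes an SAE and goes to the Chief Investigator within 24 hours, apart from the elective admissions already exempted. The class sent to the ethics committee and Sponsor is still related, unexpected SAEs, as 5.2.2 now states.

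**The case against.** The strongest reply is that the affected set may be empty. The only explanation of *unexpected* in the protocol is the one in 5.2.2. With no listed expected serious event, every death, arrest or unplanned admission counts as unexpected, is an SAE under 5.1, and goes to the Chief Investigator within 24 hours. Sections 3.3 and 3.4 name outcomes to be followed; they do not declare them expected. This largely stands, and it is why the point is minor. It does not remove the inconsistency, because 5.1 does not say that it borrows the meaning in 5.2.2.

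A second reply is that the surrounding text shows a drafting slip that sites would read through: 5.2.2 filters SAEs by expectedness, it exempts elective admissions that would typically be foreseen anyway, and 5.2 sends questions to the Chief Investigator. That is probably right about intent. It also supports correcting the definition.

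Two stronger readings are tempting, and the protocol does not support either.

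- *Expected serious events escape reporting altogether.* They do not. Section 5.2 requires all adverse events to be reported, and on one reading 5.2.1 requires these to be recorded. What can be lost is the SAE form and the 24-hour limit.
- *Study C loses outcome events.* It does not. Section 6 collects follow-up through the electronic health record and clinical device checks until 1 April 2027, independently of SAE forms.

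It is also fair to say that the procedures are non-invasive recordings and that section 3.3 states there are no significant risks, so related SAEs should be rare.

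**Conclusion.** The inconsistency between 5.1 and 5.2.2 is real and rests on exact wording. Read literally, a serious event regarded as expected triggers neither the SAE form nor the 24-hour notice, whichever way *non-serious* is read. The size in practice ranges from no events, if the meaning in 5.2.2 governs 5.1 and no list of expected serious events exists, to an unknown number, if sites apply their own judgement. The first end of that range assumes that the available text is complete on this point.

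The consequence is confined to how quickly and formally the Chief Investigator learns of such events. No endpoint, sample size or analysis is affected. Severity: minor.

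**What to change.** Delete the words *and unexpected* from the SAE definition in section 5.1. Leave expectedness only in 5.2.2, where it decides which SAEs go to the ethics committee and the Sponsor. No other section needs to change.

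The cost is a two-word edit and possibly a few more SAE forms to the Chief Investigator. In return, the judgement on expectedness is made by the person to whom 5.2.2 assigns it, after the event has been notified.
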